### **Schedule of Research Activities**

\*urine culture required if urinalysis is positive for Leukocytes, positive cultures will be treated by the study physicians per standard of care.

All PTNS or sham sessions will be completed by an experienced Urology Research Nurse. The methods described by Peters et al in the SUMiT study will be utilized.

#### **ACTIVE PTNS GROUP:**

Position: Patients will be placed in a comfortable position, sitting or supine. The treatment leg will be propped up comfortably on a foot rest but draped and out of view from the patient.

Needle: A 34-gauge needle electrode will be inserted at a 60-degree angle approximately 5 cm cephalad to the medial malleolus and slightly posterior to the tibia (Fig. 1a in the appendix).

Electrode Pads: A PTNS surface electrode will be placed on the ipsilateral calcaneus as well as 2 inactive sham surface electrodes, 1 under the little toe and 1 on the top of the foot. When the PTNS lead set is connected to the Urgent PC stimulator, a current level of 0.5 to 9 mA at 20 Hz was selected based on each patient's foot and plantar motor and sensory responses.

Duration: This treatment will be maintained 60 minutes. The patient will be given a brief break between sessions. To complete the 120-minute session, the same treatment will be performed on the patient's other foot for 60 minutes.

#### **SHAM GROUP**

Since patients in the active arm will feel foot stimulation, the sham arm will mimic this feeling without the tibial nerve being stimulated.

Position: The leg and foot will be draped and out of view from the patient. The patient will be placed in a comfortable position, supine or sitting, for easy access to the sham insertion site; for example, the patient may sit with the soles of the feet together and knees abducted and flexed.

Needle: The medial aspect of the lower extremity will be palpated and the tibial nerve site will be identified approximately 5 cm cephalad from the medial malleolus. A Streitberger needle will be used at the tibial nerve insertion site as described above to simulate needle placement without puncturing the skin. The needle will be taped in place.

Electrode Pads: Three electrodes will be placed on the patient's foot, two active TENS electrodes and one inactive TENS electrode. The TENS "grounding pad" will be a gel electrode pad from a TENS unit device that is placed on the bottom of the foot just below the smallest toe. Another gel electrode will be placed on the top of the foot just above the small toe for conduction. These two electrodes will be connected to the TENS unit lead wires for

sham stimulation. A third, inactive, gel electrode, will be placed near the medial aspect of the calcaneus to mimic the PTNS treatment. Care must be taken to avoid reflexology areas for major organs as the electrode pads are placed. All TENS electrodes are reusable and may be designated for individual patients.

Test and Therapy: The TENS electrode will be connected by lead wires to the Biostim M7 TENS (Biomedical Life Systems, Vista CA) unit or equivalent set at 20 HZ. The TENS unit will be turned on and stimulation slowly increased to the patient's first sensory level.

Duration: This treatment will be maintained 60 minutes. The patient will be given a brief break between sessions. To complete the 120-minute session, the same treatment will be performed on the patient's other foot for 60 minutes.

#### IV. Risks and Benefits

##### *PTNS or Sham Treatment*

###### **Less frequent (occurring from 1% to 10% of the time):**

- Discomfort/pain/pressure/tingling at, or near, the stimulation site, or the subject's lower leg or foot
- Redness/inflammation at, or near, the stimulation site
- Possible worsening of OAB symptoms (Stimulating the nerves can either improve, worsen, or have no effect on symptoms) i.e. increased frequency, urgency, nocturia/ leaking due to the procedure

###### **Rare (occurring less than 1% of the time):**

- Skin irritation
- Electrode burn
- Allergic reaction to adhesive pad gel
- Numbness of toes
- Allergic Reaction
- Possible increase in lower extremity pain or pelvic pain

**If a patient is required to turn off their InterStim or complete a "washout" period to participate in the study there is a chance they may return to baseline urinary symptoms. This may include but is not limited to an increase in urinary frequency, urgency, and urinary leakage.**

## V. Eligibility Criteria

### Inclusion criteria:

- Women and men  $\geq$  18 years of age
- Self-reported failed conservative care of behavioral modifications and / or oral medications
- A score of  $\geq$  4 on question 1 of the OAB-q symptom bother short form completed by the patient at screening
- Average urinary frequency of  $\geq$  8 voids per day as recorded on initial 3-day voiding diary
- Self-reported bladder symptoms  $\geq$  3 months
- On a stable dose of antimuscarinics/beta-3 agonists for  $\geq$  4 weeks, and willing to remain on the medication for the duration of the study OR discontinued antimuscarinics/beta-3 agonists for  $\geq$  2 weeks
- Capable of giving informed consent
- Ambulatory and able to use toilet independently without difficulty
- Capable and willing to follow all study-related procedures

### Exclusion criteria:

- Pregnant or planning to become pregnant during study duration
- Diagnosis of neurogenic bladder
- Botox use in bladder or pelvic floor muscles within past 12 months
- Pacemakers or implantable defibrillators
- Current urinary tract infection
- Active use of neuromodulation in any other form. If patient has InterStim, must be turned off for 2 weeks for a washout period and remain off during the entirety of the study.
- Current use of Transcutaneous Electrical Nerve Stimulation (TENS) in pelvic region, back or legs
- Previous PTNS treatment who received greater than 6 treatments. Those who have received less than 6 treatments will be allowed to screen if the last treatment was at least 6 months prior to screening.
- Use of investigational drug/device therapy within past 4 weeks
- Participation in any clinical investigation involving or impacting gynecologic, urinary or renal function within past 4 weeks
- Current or past history of any physical condition that, in the investigator's opinion, might put the subject at risk or interfere with study results interpretation (i.e. pelvic cancer or pelvic radiation treatment)

## VI. Data Analysis

A biostatistician will perform all statistical analyses using SAS or similar statistical software. Descriptive statistics will be calculated. A completer analysis will be conducted for those who finish the study per protocol. The primary endpoint will be assessed comparing GRA responses between sham and PTNS groups at one week ( $\pm$  3 days) post induction. This comparison will also be made for all other visits using t-tests or chi-square tests, as appropriate.

Secondary endpoints will include comparisons between sham and PTNS groups looking at variables in the 3-day voiding diary and OABq-SF at one week ( $\pm$  3 days) post-induction.

Changes from baseline will also be analyzed. This comparison will also be made for all other visits using appropriate statistical tests.

Other statistical analyses will be completed as appropriate.

An intent to treat analysis which will identify any subject not assessed at 12 weeks post-induction as a failure will be conducted; a minimum of 1 induction treatment will be required to be included in the analysis.

Calculating Sample Size:

A sample size estimate of approximately 64 patients, 32 per study arm, was calculated using the Z test with pooled variance using a 58.3% responder rate in the PTNS group and a 21.9% responder rate in the sham group with a 5% significance level and 80% power; this also accounts for a 10% drop out rate. (Peters et al reported 58.3% and 21.9% responder rates for PTNS and sham groups respectively for an as-followed completer analysis and 54.5% and 20.9% responder rates for PTNS and sham groups respectively with an intent to treat analysis. We used the as-followed responder rates in calculating our sample size.)

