## I. Background and Rationale

Overactive bladder (OAB) is a common condition with a prevalence ranging from 5.9% to 16.9% in the United States and has been found to increase with age. OAB has a negative impact on health related quality of life (QoL), and OAB patients have more anxiety and depression than controls. Primary treatment for OAB include behavioral modifications, such as decreased caffeine intake and timed voiding, and pelvic floor physical therapy. Second line therapy includes anticholinergic medicine/beta-3 adrenoceptor agonists. Unfortunately, compliance and adherence to these medications decreases over time likely due to side effects and/or efficacy.

Per AUA/SUFU guidelines, PTNS is a third line recommendation for OAB along with onabotulinumtoxinA (BTX) injection and sacral neuromodulation. The overall objective success (defined as  $\geq 50\%$  decrease in urge or urge urinary incontinence (UI) and 25% reduction in daytime and/or nighttime frequency) of PTNS has been published and ranges from 60% to 71%.

In the single sham-controlled trial (SUMiT: n=220), Peters et al reported that 54.5% of PTNS subjects had moderately or markedly improved bladder symptoms on global response assessments (GRA) compared to 20.9% of sham subjects ( $p < 0.001$ ). PTNS subjects also had statistically significant improvements in frequency, nighttime voids, voids with moderate to severe urgency and UI episodes compared to sham. Furthermore, significant improvements in bladder symptoms on GRA and quality of life (QoL) as measured with the Overactive Bladder Questionnaire (OABq) were observed after 12 but not 6 treatments, providing support for a 12-week treatment course. In another randomized, placebo controlled trial, Finazzi et al showed 71% response rate in the PTNS group compared to 0% in the sham, placebo group.

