At 4, 8, and 12 weeks post-induction ( $\pm$  7 days), patients will return for follow-up appointments. Non-modified OAB-q SF, GRA and 3-day voiding diary will be collected and a urinalysis completed. Maintenance treatments (sham or active PTNS depending on treatment arm) will be given. Maintenance treatment will consist of a 30 minute treatment per standard of care. We will also assess for adverse events and concomitant medications at each of these visits.

After all study activities are complete, patients will be un-blinded at week 12 marking the end of the study. Those who were in the sham arm will be offered the opportunity to continue on to the open label phase of the study. Subjects in the open label phase will be offered the same accelerated treatments as those in the initial active PTNS treatment group. They will have up to 12 weeks to decide if they would like to continue on to the open label phase. This option will also be offered to those who had been previously randomized to the Sham group prior to the protocol amendment, even if they have completed their visit schedule. The follow up schedule will also be conducted in the same manner. Either of the groups can be offered re-induction per insurance requirements if they elect to do so with their

physician or can seek alternative treatments (BTX, sacral neuromodulation, etc.) per standard of care.

Our goal is to have patients complete all three open label treatments within one week (7 days) again, as there are always impedances (scheduling conflicts, illness, etc.) we will allow patients to complete all treatments within 2 weeks (14 days) if necessary. Patients will be allowed back-to-back treatments (i.e. two days in a row) if they should elect to do so. Adverse events and concomitant medications will be assessed at each treatment whether sham or active PTNS. GRA will be gathered at each visit beginning with the second induction treatment.

After completing the one-week open label induction consisting of three active treatments, patients will receive a phone call three days ( $\pm$  1 day) after the last treatment to assess for any adverse events as well as remind them to start filling out their 3 day diary if they have not already begun to do so. This will also serve as a reminder phone call for their upcoming appointment.

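### Primary endpoint is GRA at week 1, but both planned analysis sets depend on week 12, so observed week-1 responses can be dropped or scored as failures, and neither set is named decisive

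*Combined protocol and SAP*

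**What the plan says.** All of the following is in Section VI unless noted.

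- **Primary endpoint.** "The primary endpoint will be assessed comparing GRA responses between sham and PTNS groups at one week" after induction, with a window of ±3 days. Section II says the same, and Section III collects GRA at that visit.
- **First analysis set.** "A completer analysis will be conducted for those who finish the study per protocol". Section III fixes the end of the study: "After all study activities are complete, patients will be un-blinded at week 12 marking the end of the study".
- **Second analysis set.** "An intent to treat analysis which will identify any subject not assessed at 12 weeks post-induction as a failure will be conducted". The entry condition is that "a minimum of 1 induction treatment will be required to be included in the analysis".
- **Sample size.** 32 per arm, from 58.3% versus 21.9%, a 5% significance level, 80% power and 10% dropout. The protocol explains: "We used the as-followed responder rates in calculating our sample size". It also reports the cited sham-controlled trial's intent-to-treat rates, 54.5% and 20.9%.

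No section gives a missing-data rule for the week-1 visit or says which of the two analyses decides the trial.

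**The concern.** Staying to week 12 is settled after randomisation and after the primary outcome has been measured. Visits with maintenance treatment at weeks 4, 8 and 12 lie between the endpoint and the point that fixes who is analysed and how. If later dropout differs by arm, or by arm and response together, it can shift the week-1 comparison in at least one of the sets, even though the week-1 data are in hand.

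Making the planned intent-to-treat analysis primary would not cure this, because its failure rule is also tied to week 12. Purely random late loss creates no bias but still costs power: the completer set loses patients, and the failure rule turns observed responders into failures. Leaving two sets with no stated hierarchy also leaves room to choose between them after the results are known.

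**Working it through.** **Inputs from the protocol (Section VI).** Response 58.3% PTNS and 21.9% sham (as-followed); 54.5% and 20.9% (intent to treat); pooled-variance Z test; 5% significance; 80% power; 10% dropout. Sidedness is not stated, but two-sided reproduces the sample size.

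**Assumptions not in the documents.** The timing and pattern of loss, and a 40% response rate for the no-effect scenarios.

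**1. Reproduce the sample size.**

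n = [1.96·√(2p̄(1−p̄)) + 0.8416·√(p₁q₁+p₂q₂)]² / (p₁−p₂)²

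Here p̄ = 0.401, √(2×0.401×0.599) = 0.6931, √(0.2431+0.1710) = 0.6436 and p₁−p₂ = 0.364. So n = (1.3585+0.5416)²/0.1325 = 27.2, i.e. 28 per arm. Then 28/0.9 = 31.1, i.e. 32 per arm and 64 in total. The stated figure reproduces.

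**2. Power under each rule.** True week-1 rates 58.3% and 21.9%, random 10% loss in both arms, all after week 1.

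Power = Φ{[(p₁−p₂)√n − 1.96·√(2p̄(1−p̄))] / √(p₁q₁+p₂q₂)}

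- Every week-1 GRA used, 32 per arm: (2.0591−1.3585)/0.6436 = 1.089, so 86.2% (exact 87.4%).
- Completers, 29 per arm: (1.9602−1.3585)/0.6436 = 0.935, so 82.5% (exact 81.8%).
- Week-12 failure rule, 32 per arm: the rates become 0.9×58.3 = 52.5% and 0.9×21.9 = 19.7%, and the difference falls from 36.4 to 32.8 points. (1.8532−1.3312)/0.6385 = 0.818, so 79.3% (exact 80.5%).

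At the cited intent-to-treat rates, 32 per arm gives 80.7% (exact 82.0%).

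Unequal loss under the week-12 rule moves the result either way. With 5% PTNS and 15% sham lost, the difference is 36.8 points and power 88.0%. With 15% and 5%, it is 28.7 points and 68.1%.

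**3. Rejection rate with no true effect.** Simulation of 400,000 trials per pattern, 32 per arm, uncorrected chi-square at two-sided 5%, 40% true response in both arms, all loss after week 1.

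| Loss pattern | Completers | Week-12 failure rule | Either set | Week-1 rule |
|---|---|---|---|---|
| (1) Random 10% in both arms | 5.2% | 5.3% | 6.4% | 5.6% |
| (2) Unrelated to response: 5% active, 15% sham | 5.2% | 6.6% | 8.1% | 5.5% |
| (3) Both arms: 5% of responders, 20% of non-responders | 5.2% | 5.4% | 6.8% | 5.6% |
| (4) Pattern (3) in active, reversed in sham | 9.8% | 8.2% | 11.1% | 5.5% |

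The expected rates behind these results are:

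- Pattern (2), failure rule: 0.40×0.95 = 38% versus 0.40×0.85 = 34%.
- Pattern (4), completers: active 0.38/(0.38+0.60×0.80) = 0.38/0.86 = 44%; sham 0.32/(0.32+0.60×0.95) = 0.32/0.89 = 36%.
- Pattern (4), failure rule: 0.40×0.95 = 38% versus 0.40×0.80 = 32%.
- Patterns (1) and (3): no gap between arms in either set.

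The Either set column assumes success is claimed if either analysis is significant. At 21.9% response, pattern (1) gives 5.1%, 5.1%, 5.9% and 5.1% in the same column order.

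**The case against.** **The failure rule may be meant for week 12 only.** Its sentence names no comparison, comes last in the analysis text and mentions only week 12. On that reading no week-1 response is recoded. The ambiguity is real, but it does not rescue the plan: the primary endpoint would then have no intent-to-treat rule, and the only other set would still depend on finishing the study. The link from finishing to week 12 is inferred from Section III, and adherence to protocol is not defined, so the text needs correcting on either reading.

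**The text leans towards completers.** The completer sentence directly precedes the primary comparison, and the sample size uses as-followed rates. That is a hint, not a designation. It is fair, however, that nothing in the protocol says success would be claimed on whichever set is significant, so the either-set figures show exposure rather than plan.

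**The bias is small outside extremes.** This stands. Patterns (1) and (3) show no inflation beyond the 5.6% of the week-1 rule, and pattern (2) raises only the failure rule. Pattern (4) needs opposite response-related dropout by arm among patients meant to remain blinded. If missing patients were scored as failures in the cited trial (an assumption), its rates imply losses of 1−54.5/58.3 = 6.5% in PTNS and 1−20.9/21.9 = 4.6% in sham: low, nearly balanced, and in the opposite direction to pattern (2). Simulating about that loss gives type I error near 5.2% (completers) and 5.4% (failure rule), with power 84.5% and 82.1%. That is a different trial and schedule, so it is indicative only.

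**The power loss is modest.** This also stands. The plan promised 80%, and on exact calculation the failure rule still gives 80.5%. The gain from a week-1 rule depends on how much loss comes after week 1.

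**Conclusion.** The concern holds. The primary outcome is fixed at week 1 while both analysis sets turn on week 12, so the plan as written discards or misclassifies observed primary outcomes, and it does not say which analysis decides. The sample size itself is correct.

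With random 10% loss after week 1, the cost is about 4 points of power in completers (86.2% to 82.5%) and about 7 under the failure rule (86.2% to 79.3%). Type I error is essentially unaffected by benign loss, rises to 6.6% under the failure rule with 5% versus 15% loss, and reaches 8.2% to 9.8% only in the near-worst case. A week-1 rule stays at 5.5% to 5.6% throughout.

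These sizes rest on the assumed 40% response and the assumed loss patterns. The protocol gives one dropout figure, with no timing and no split by arm. The change should be made because it is cheap and uses data already collected, not because serious bias is likely.

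**What to change.** Name one primary analysis in Section VI:

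- **Population:** all randomised patients with at least one induction treatment, which is the condition already planned.
- **Outcome:** GRA moderately or markedly improved at week 1. This matches the definition behind the cited rates; Section I reports that "54.5% of PTNS subjects had moderately or markedly improved bladder symptoms on global response assessments".
- **Missing data:** only a missing week-1 GRA counts as non-response.
- **Test:** chi-square at two-sided 5%, which corresponds to the pooled Z test used for sizing.

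Keep the completer analysis, the week-12 failure rule and any t-test on GRA scores as supportive. The week-12 failure rule belongs with the week-12 comparison.

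State power at 32 per arm as about 79% if all 10% loss comes before week 1 and about 86% if it all comes after, with 80.7% at the cited intent-to-treat rates.

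The cost is wording only, and N stays at 64. The downside is that the expected difference becomes 32.8 to 36.4 points, depending on how much loss precedes week 1, instead of a fixed 36.4. If all of it does, power is 79.3% by the normal approximation (80.5% exact).

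### Section VI applies a completer and an intent-to-treat analysis to the same week-1 GRA endpoint without saying which decides, and the completer set depends on events up to 11 weeks after that endpoint

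*Combined protocol and SAP*

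**What the plan says.** The primary endpoint, in section II (Objectives and Endpoints) and again in section VI (Data Analysis), compares GRA responses between sham and PTNS one week after induction. Neither place names an analysis set.

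Section VI then gives two analyses:

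- Directly before the primary-endpoint sentence: "A completer analysis will be conducted for those who finish the study per protocol". Section III (Methodology) puts the end of the randomized study at the week-12 visit, so a completer is someone followed to week 12.
- After the secondary endpoints: "An intent to treat analysis which will identify any subject not assessed at 12 weeks post-induction as a failure will be conducted". Membership requires at least one induction treatment.

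Neither is called primary, supportive or sensitivity, and no rule covers disagreement between them.

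The sample-size paragraph assumes a "58.3% responder rate in the PTNS group and a 21.9% responder rate in the sham group". It takes a level of 5% and power of 80%, and allows for 10% dropout. It quotes the earlier sham-controlled trial's "54.5% and 20.9% responder rates for PTNS and sham groups respectively with an intent to treat analysis" but adds: "We used the as-followed responder rates in calculating our sample size".

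**The concern.** One endpoint with two unranked analyses has no defined result when they disagree. The position of the completer sentence and the choice of sizing rates both lean towards completers, so a reader following section VI could take that analysis as decisive.

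The completer set is selected after randomization. A patient with a valid week-1 GRA who leaves at week 6 is removed from the completer comparison of week-1 GRA. Read literally, the same patient becomes a failure under intent-to-treat, whatever the week-1 answer was. Events up to 11 weeks after the endpoint (12 − 1) can therefore change the primary verdict. Patients without benefit have an obvious reason to leave. If they leave one arm more than the other, the completer comparison is biased.

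**Working it through.** **Inputs from section VI.** Pooled-variance Z test, 5% level, 80% power, 10% dropout, 32 per arm; completer rates 58.3% vs 21.9%; intent-to-treat rates 54.5% vs 20.9%. Sidedness is not stated. Two-sided is assumed because it reproduces the stated number (one-sided gives 25 per arm after inflation).

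**1. Reproduce the stated size.**

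n per arm = [1.960·√(2p̄(1−p̄)) + 0.8416·√(p₁(1−p₁) + p₂(1−p₂))]² / (p₁−p₂)²

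Completer rates, p̄ = 0.401: (1.960 × 0.6931 + 0.8416 × 0.6435)² / 0.364² = 27.25, so 28. Then 28/0.9 = 31.1, so 32 per arm and 64 in total. This matches the protocol.

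**2. The same formula at the quoted intent-to-treat rates.** p̄ = 0.377: (1.960 × 0.6854 + 0.8416 × 0.6429)² / 0.336² = 31.45, so 32 per arm. Dropouts stay in as failures, so no inflation is needed.

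Power at 32 per arm = Φ[(0.336·√32 − 1.960 × 0.6854)/0.6429] = Φ(0.867) = 80.7%.

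If instead the completer rates are cut by 10% failures in each arm (52.5% vs 19.7%), power is 79.3%.

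**3. One data set, two verdicts.** Take 32 per arm, 28 active and 29 sham completers (7 of 64 lost, 10.9%), with 14 and 7 responders among them.

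- Completers: 14/28 vs 7/29; difference 0.2586, SE 0.1278, z = 2.02, p = 0.043.
- Intent-to-treat, losses as failures: 14/32 vs 7/32; difference 0.2188, SE 0.1174, z = 1.86, p = 0.062.

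Section VI does not say whether this trial succeeded.

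**4. How often, and with what error.** Simulation of 400,000 trials per row, 32 per arm, pooled Z test, two-sided 5%. Dropouts are excluded from the completer test and scored as failures in intent-to-treat. All dropout patterns are assumptions.

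| True rates (active / sham) | Dropout | Completer significant | Intent-to-treat significant | Verdicts differ |
|---|---|---|---|---|
| 58.3% / 21.9% | 10% both arms, random | 83% | 80–81% | 5.8% (4.0% completer only) |
| 58.3% / 21.9% | 20% both arms, random | 78% | 73% | 10.1% (7.8% completer only) |
| 58.3% / 21.9% | 15% active, 5% sham, random within arm | 82.7% | 69.6% | 13.3% (13.2% completer only) |
| 21.9% / 21.9% | 10% both arms, random | 5.1% | 5.1% | 1.5% |
| 21.9% / 21.9% | 13% of non-responders, both arms | about 5% | about 5% | 1.7% |
| 21.9% / 21.9% | 20% of active non-responders, no active responders, 5% of sham | 6.7% | 5.2% | 3.5% |
| 21.9% / 21.9% | 25% of active non-responders, no active responders, 5% of sham | 7.7% | 5.2% | 5.0% |

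In the fourth row, counting the trial positive if either analysis is significant gives 5.9%.

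**The case against.** Several stronger readings are tempting, and the documents do not support them.

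- *Sizing on completer rates leaves intent-to-treat underpowered.* It does not. The protocol states openly which rates it used, and the same 64 patients give 80.7% power at its own intent-to-treat rates.
- *Two unranked tests break the 5% error rate.* Barely, under equal random dropout: 5.9% against a baseline of 5.1%. The exposure comes from selective dropout, not multiplicity.
- *Frequent disagreement means false claims.* The 13.3% with dropout of 15% active and 5% sham arises under a true effect with dropout random within each arm, where the completer comparison is unbiased. Nearly all of it is true effects that failure imputation misses.
- *The protocol makes the completer analysis primary.* It does not say so. Order and sizing suggest it, no more.

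The objection to the selective-dropout scenario is also fair. It implies losing 0.781 × 20–25%, or about 16–20%, of the active arm, against a planned 10%. The documents give no specific reason for such asymmetry: legs are draped, sham sensation is imitated, and unblinding waits until week 12. When non-responders leave both arms equally, completer error stays at about 5%.

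Finally, intent-to-treat as written is no clean alternative. Its failure rule looks at week 12, and its minimum of one treatment makes it a modified set. Promoting it unchanged could turn observed week-1 responders into failures.

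None of this supplies the missing ranking.

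**Conclusion.** The concern holds in this limited form: section VI does not say which analysis decides the primary week-1 GRA comparison, and the one it lists first and sizes for is selected by events up to week 12. At the planning rates with 10% random dropout, about 6% of trials would have two conflicting verdicts. The completer false-positive rate reaches about 7–8% only if active non-responders leave selectively (20–25%, with sham losing 5%); intent-to-treat then stays near 5%. With equal dropout the inflation is negligible.

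These figures assume a two-sided test, a binary GRA response, all 32 per arm receiving at least one treatment, and dropout patterns that the documents do not give. The absence of a ranking rests on the text alone.

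**What to change.** In section VI:

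1. State that the intent-to-treat comparison of week-1 GRA response is the single confirmatory analysis.
2. For that comparison, count a patient as a failure when the week-1 GRA is missing. Keep the week-12 rule for week-12 outcomes.
3. Acknowledge that requiring at least one induction treatment makes this a modified intent-to-treat set.
4. Label the completer analysis supportive, not sufficient by itself for an efficacy claim.
5. Optionally, note that 32 per arm gives about 81% power at 54.5% vs 20.9%.

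The cost is a few sentences and no extra patients, but it is not nil. The sponsor gives up a claim based on completers alone. Failure imputation also loses power if dropout is heavier in the active arm: about 70% if 15% of active and 5% of sham patients lack the week-1 GRA. Tying the rule to week 1 limits this loss, because later departures no longer count against the primary endpoint.
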